### 6.2 Inclusion criteria

For an eligible subject, all inclusion criteria must be answered “yes”.

1. Informed consent obtained before any trial-related activities. Trial-related activities are any procedures that are carried out as part of the trial, including activities to determine suitability for the trial
2. Confirmed diagnosis of Prader-Willi Syndrome (by genetic testing)
3. Male or female, age at the time of signing informed consent:
  - Part A:  $\geq 12$  and  $< 18$  years
  - Part B:  $\geq 6$  and  $< 12$  years
4. Tanner stage 2–5 pubertal development for part A, and Tanner stage below 2 (defined as Tanner stage 1 with or without premature adrenarche) for part B
5. BMI corresponding to  $\geq 30$  kg/m^2 for adults by international cut-off points  and  $\geq$  the 95th percentile for age and sex (for diagnosis of obesity) (please refer to [Appendix A](#))
6. Stable body weight during the previous 90 days before screening ( $< 10$  kg self-reported weight change)
7. Testing has been performed to evaluate for adrenal insufficiency and documented in medical record

### 6.3 Exclusion criteria

For an eligible subject, all exclusion criteria must be answered "no".

1. Type 1 diabetes mellitus (T1DM)
2. Type 2 diabetes mellitus (T2DM)
3. No change in treatment plan with growth hormone (GH) from randomisation to the end of the open-label period (patients on growth hormone to stay on, patients off GH to stay off during this period. Adjustments in doses of growth hormone will be permitted)
4. Calcitonin  $\geq 50$  ng/L (please refer to [Appendix C](#))
5. Family or personal history of Multiple Endocrine Neoplasia Type 2 (MEN2) or Medullary Thyroid Carcinoma (MTC)
6. History of pancreatitis (acute or chronic)

Protocol: Liraglutide  
Trial ID: NN8022-4179  
UTN: U1111-1162-7884  
EudraCT no.: 2014-004415-37

**CONFIDENTIAL**

Date: 16 July 2020  
Version: 5.0  
Status: Final  
Page: 37 of 125

**Novo Nordisk**

7. Treatment with any medication prescribed for weight loss within 90 days before screening (e.g. Orlistat, zonisamide, topiramate/phentermine, lorcaserin, phentermine, bupropion/naltrexone, liraglutide, metformin)
8. Diet attempts using herbal supplements or over-the-counter medications within 90 days before screening
9. Participation in an organised weight reduction programme (e.g. Weight Watchers®) within 90 days before screening
10. Previous surgical treatment for obesity (excluding liposuction if performed > 1 year before screening)
11. History of major depressive disorder within 2 years before randomisation
12. History of other severe psychiatric disorder (e.g. schizophrenia, bipolar disorder)
13. Part A only: PHQ-9 score of  $\geq 15$  at screening
14. Part A only: Any suicidal ideation of type 4 or 5 in the last 30 days prior to screening based on the C-SSRS questionnaire
15. Any lifetime history of suicidal attempt
16. Any suicidal behaviour within 30 days before randomisation
17. Surgery scheduled for the trial duration period except for minor surgical procedures, at the discretion of the investigator
18. Subjects with confirmed bulimia nervosa disorder
19. Uncontrolled treated or untreated hypertension >99th percentile for age and gender in children (please refer to [Appendix B](#)). If white-coat hypertension is suspected at the screening V2 a repeated measurement at V3 prior to other trial related activities is allowed (last measurement being conclusive)
20. Diagnosis of malignant neoplasms within the last 5 years (except basal and squamous cell skin cancer, polyps and in-situ carcinomas)
21. Known or suspected abuse of alcohol or narcotics
22. Known or suspected hypersensitivity to trial product(s) or related products
23. Previous participation in this trial. Participation is defined as being randomised
24. Receipt of any investigational medicinal product within 30 days before screening or participation in another trial within 30 days before screening
25. Female who is pregnant, breast-feeding or intends to become pregnant or is of child-bearing potential not using adequate contraceptive methods (adequate contraceptive measures as required by local regulation or practice).
26. Any condition which, in the opinion of the investigator might jeopardise subject's safety or compliance with the protocol
27. Untreated adrenal insufficiency (please refer to Section [8.1.1.1](#))
28. Suggestive history of, or significant risk of gastroparesis (e.g. marked abdominal bloating post meal, history of vomiting, severe constipation), as judged by the Investigator

The inclusion and exclusion criteria will be checked prior to subject randomisation.

Protocol: Liraglutide  
Trial ID: NN8022-4179  
UTN: U1111-1162-7884  
EudraCT no.: 2014-004415-37

CONFIDENTIAL

Date: 16 July 2020  
Version: 5.0  
Status: Final  
Page: 38 of 125

Novo Nordisk

#### 6.4 Discontinuation of trial product criteria

The subject must discontinue trial product if the following applies:

1. Due to a safety concern at the discretion of the investigator
2. Non-compliant with trial procedures at the discretion of the investigator.
3. Pregnancy
4. Intention of becoming pregnant
5. Participation in another clinical trial throughout the trial
6. Included in the trial in violation of the inclusion and/or exclusion criteria
7. Diagnosis of acute pancreatitis (section [8.6.3.3](#) and [8.6.2](#))
8. Diagnosis of medullary thyroid carcinoma
9. Weight loss attempts other than what is agreed with the dietitian as part of the trial intervention
10. If diabetes treatment other than diet, physical activity and metformin addition is initiated.
11. Initiation of treatment that based on the investigator's judgement may cause significant weight change. This should also include treatment with any of the following medications: orlistat, zonisamide, topiramate, lorcaserin, phentermine, bupropion, naltrexone or GLP-1 receptor agonists
12. Inadequate psycho- and/or pharmaco therapeutic treatment of a subject's psychiatric disorder (section [8.5.10.3](#))
13. The subject and/or the subject's LAR refuse referral to a mental health professional (MHP) and it in investigator's opinion, it is unsafe for the subject to continue in the trial (section [8.5.10.3](#))
14. Due to safety reasons if at the recommendation of the external DMC and endorsed by the safety committee.
15. If a subject treated with the individual weight-based starting dose experiences unacceptable intolerance as judged by the investigator, the subject must be discontinued from trial product (Section [8.1.8](#))

See section [8.1.8](#) for how to handle discontinuation of trial product.

#### 6.5 Withdrawal criteria

1. The subject may withdraw at will at any time either by the subject or by the subject's parent or the subject's legally acceptable representative. The subject's request to discontinue must always be respected

See section [8.1.9](#) for how to handle withdrawals.

#### 6.6 Subject replacement

Subject replacement will be initiated if the actual withdrawal rate is higher than assumed (10% at week 16 and 20% at week 52) to ensure the number of evaluable subjects required by PDCO will be met.

Protocol: Liraglutide  
Trial ID: NN8022-4179  
UTN: U1111-1162-7884  
EudraCT no.: 2014-004415-37

~~CONFIDENTIAL~~

Date: 16 July 2020  
Version: 5.0  
Status: Final  
Page: 39 of 125

**Novo Nordisk**

The trial will continue until at least 45 evaluable subjects are included in total, divided as:

- Part A, at least 28 evaluable subjects
- Part B, at least 17 evaluable subjects
  - and of these subjects at least 5 need to be below 9 years of age.

## 6.7 Rationale for trial population

PWS is a rare genetic disease with an estimated incidence of 1:15,000 to 1:25,000 live births, therefore the number of subjects planned for this trial is relatively small.

Obesity is the major cause of morbidity and mortality in patients with PWS. The diagnosis of obesity in adolescents and children is based on BMI corresponding to  $\geq 30$  kg/m^2 for adults by international cut-off points and  $\geq 95$ th percentile for age and sex for children.

Subjects are required to have had testing performed to evaluate for adrenal insufficiency. This must be documented in their medical records to confirm adrenal sufficiency, see section [8.1.1.1](#).

Hypogonadism and growth hormone insufficiency (causing short stature) are commonly seen in patients with PWS, suggesting that pituitary hormones are affected by the disease. The secretion of cortisol, the main adrenal glucocorticoid in humans is under the control of pituitary adrenocorticotrophic hormone (ACTH). Adrenal insufficiency has been reported, and although uncommon in patients with PWS, the clinical manifestations are serious. Therefore it is important to ensure patients enrolled in the trial have had testing performed to evaluate for adrenal insufficiency, and that those who have this condition are under treatment.

As previously mentioned, subjects may enter the trial on GH therapy as short stature associated with PWS is an approved indication for GH therapy. It has been reported that in children with PWS, 8 years of GH treatment resulted in completely normalised height and head circumference, and a significant increase in lean body mass during the first year, and remained stable for 7 years at a level above baseline. It is well known that growth hormone may affect glucose metabolism, and may increase fasting plasma glucose. Therefore, no change in GH treatment plan should be made during the trial, and subjects not using GH therapy will stay off during the trial. Adjustments in doses of growth hormone are permitted.

As mentioned previously in section [3.1](#), there is limited information on the safety and effectiveness of pharmacotherapy in controlling appetite and obesity in PWS patients, especially in children and adolescents with PWS. There is a knowledge gap and lack of treatment options for weight loss/improvement in the weight-related symptoms and risk factors in PWS population. Therefore the current trial has been mandated by PDCO and will provide useful information on using liraglutide as a therapeutic option for weight management in this patient population.

Protocol: Liraglutide  
 Trial ID: NN8022-4179  
 UTN: U1111-1162-7884  
 EudraCT no.: 2014-004415-37

~~CONFIDENTIAL~~

Date:  
 Version:  
 Status:  
 Page:

16 July 2020  
 5.0  
 Final  
 40 of 125

**Novo Nordisk**

## 7 Milestones

### 7.1 Part A

Planned duration of recruitment period (FPFV– LPFV):	72 weeks
Planned date for first patient first visit (FPFV):	09-Nov-2015
Planned date for first patient first treatment: (FPFT)	23-Nov-2015
Planned date for last patient first visit (LPFV):	27-Mar-2017
Planned date for last patient first treatment (LPFT):	10-Apr-2017
Planned date for last patient last visit (LPLV):	07-May-2018

### 7.2 Part B

Planned duration of recruitment period (FPFV– LPFV):	64 weeks
Planned date for first patient first visit (FPFV):	09-Apr-2018
Planned date for first patient first treatment: (FPFT)	23-Apr-2018
Planned date for last patient first visit (LPFV):	01-Jul-2019
Planned date for last patient first treatment (LPFT):	15-Jul-2019
Planned date for last patient last visit (LPLV):	10-Aug-2020

End of trial is defined as LPLV for part B.

### 7.3 Recruitment

A global recruitment strategy will be developed in cooperation with the participating countries to ensure that a sufficient number of subjects are randomised. Prior to FPFV, all sites should have a site-specific recruitment strategy in place detailing how many subjects they can recruit within a certain period.

The screening and randomisation rate will be followed closely via the interactive voice/web response system (IV/WRS) in order to estimate when to stop screening. All investigators will be notified immediately when the recruitment period ends, after which no additional subjects may be screened and the IV/WRS will be closed for further screening. All subjects included in the screening period and eligible for randomisation can be randomised.

Protocol: Liraglutide  
Trial ID: NN8022-4179  
UTN: U1111-1162-7884  
EudraCT no.: 2014-004415-37

~~CONFIDENTIAL~~

Date:	16 July 2020	Novo Nordisk
Version:	5.0	
Status:	Final	
Page:	41 of 125	

#### 7.4 Trial registration

Information of the trial will be disclosed at [clinicaltrials.gov](http://clinicaltrials.gov) and [novonordisk-trials.com](http://novonordisk-trials.com). According to the Novo Nordisk Code of Conduct for Clinical Trial Disclosure, it will also be disclosed according to other applicable requirements such as those of the International Committee of Medical Journal Editors (ICMJE), the Food and Drug Administration Amendment Act (FDAAA), European Commission Requirements and other relevant recommendations or regulations. If a subject requests to be included in the trial via the Novo Nordisk e-mail contact at these web sites, Novo Nordisk may disclose the investigator's contact details to the subject. As a result of increasing requirements for transparency, some countries require public disclosure of investigator names and their affiliations.

Protocol: Liraglutide  
Trial ID: NN8022-4179  
UTN: U1111-1162-7884  
EudraCT no.: 2014-004415-37

~~CONFIDENTIAL~~

Date: 16 July 2020  
Version: 5.0  
Status: Final  
Page: 42 of 125

**Novo Nordisk**

## 8 Methods and assessments

The following sections describe the assessments and procedures. These are also included in the flow chart (section [2](#)).

### 8.1 Visit procedures

It is the responsibility of the investigator to ensure that all site visits and phone/video conference contacts occur according to the flowchart. In order to secure consistency in data over time it is encouraged that assessments are performed consistently (e.g. using the same equipment and site staff with alike qualifications) throughout the trial.

All trial procedures must be performed as described in the protocol. Any discrepancies will result in protocol deviations and appropriate actions must be taken to avoid recurrence of the detected discrepancies.

#### 8.1.1 Screening, visit 1

Prior to any other trial related procedures, the investigator must obtain informed assent from each subject if applicable (based on age and local regulations) and informed consent from the subject's LAR(s) (section [2](#)). For information on informed assent and consent procedure see section [18.2](#).

All subjects and subject's LAR(s) must be provided with a copy of their own signed and dated informed assent form and informed consent form.

A screening session must be made in the IW/VRS. During the session each subject will be assigned a unique 6-digit subject number which will remain the same throughout the trial.

The investigator must keep a subject screening log, a subject identification code list and a subject enrolment log. The subject screening log and subject enrolment log may be combined in one list.

At screening, subjects will be provided with a card stating that they are participating in a trial and given contact address(es) and telephone number(s) of relevant trial site staff. Subjects should be instructed to return the card to the investigator at the last trial visit.

All subjects should be reminded to attend V2 in a fasting state. V2 must take place at least 1 day after V1.

##### 8.1.1.1 Adrenal insufficiency test at screening, visit 1

If the testing for adrenal insufficiency has not been performed prior to screening V1 (inclusion criterion 7), the investigator may perform a test (of their choosing) locally to evaluate for adrenal insufficiency after screening and before randomisation. The results must be available and reviewed and the subject must have initiated treatment before the randomisation visit, if applicable.

Protocol: Liraglutide  
Trial ID: NN8022-4179  
UTN: U1111-1162-7884  
EudraCT no.: 2014-004415-37

CONFIDENTIAL

Date: 16 July 2020  
Version: 5.0  
Status: Final  
Page: 43 of 125

**Novo Nordisk**

### **8.1.2 Visits attended fasting**

Fasting visits are specified in section [2](#). Fasting is defined as having consumed no food and drink except for water for the last 8 hours.

Any medication which should be taken with or after a meal should be withheld on the day of the visit until blood sampling and body weight measurements have been performed. Trial product can be taken as usual in relation to fasting visits.

In case a subject attends a fasting visit in a non-fasting state, all non-fasting measurements should be performed. The subject should return to the site in a fasting state to have fasting measurements done within the visit window for the relevant visit.

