Calcitonin 8.5.7		x											x			x			x			
Anti-liraglutide antibodies 8.5.8			x																x 	x 		
Tanner staging 8.5.9		x																	x 			
PHQ-9 and C-SSRS (part A only) 8.5.10		x																	x			
OTHER ASSESSMENTS																						
Liraglutide plasma concentration 8.7.1				x 	x 	x 		x 	x 	x 										x 		
TRIAL MATERIAL																						
Dispensing visit 9			x				x	x	x	x	x 	x 	x 	x 	x 	x 	x 	x 				
Drug accountability 9.4							x	x	x	x	x 	x 	x 	x 	x 	x 	x 	x 				

Trial Periods	Screening	Screening	Randomisation	Dose escalation			Double blind treatment	Open-label treatment								End of treatment	Follow-up	TPD 16 week FU	TPD 52 week FU			
				4	5	6		7	8	9	10 	11	12 	13	14 					15 	16	17 
Visit number	1 	2 	3	4	5	6	7	8	9	10 	11	12 	13	14 	15 	16	17 	18 	19	20	10x	19x
Timing of visit (weeks)	-2		0	1	2	3	4	8	12	16	20	24	28	32	36	40	44	48	52	54	16	52
Visit window (days)				±2	±2	±2	±2	±5	±5	±5	±5	±5	±5	±5	±5	±5	±5	±5	±5	-5	±5	±5
IV/IWRS session 10	x		x				x	x	x	x	x 	x 	x 	x 	x 	x 	x 	x 	x 			
New dose of trial product 8.1.7				x	x	x	x															
REMINDERS																						
Training in trial product & pen handling (including injection technique) 8.1.6			x	x	x	x	x	x	x	x	x 	x 	x 	x 	x 	x 	x 	x 				
Hand-out and instruct in BG meter 8.5.2.1			x																			
BG meter finger prick test 8.5.2.1			x	x	x	x	x	x	x	x	x	x	x	x	x	x	x	x	x			
Dispense dosing diary 8.7.3.1			x																			
Collect dosing diary				x	x	x		x	x	x												
Dispense hypoglycaemic episode diary 8.7.3.2			x																			
Collect hypoglycaemic episode diary				x	x	x	x	x	x	x	x	x	x	x	x	x	x	x	x			

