Dispense menstrual period diary 8.7.3.3			x																			

Protocol: Liraglutide  
 Trial ID: NN8022-4179

UTN: U1111-1162-7884  
 EudraCT no.: 2014-004415-37

Date:  
 Version:

16 July 2020 | Status:  
 5.0 | Page:

Final  
 20 of 125 | **Novo Nordisk**

Trial Periods	Screening	Screening	Randomisation	Dose escalation			Double blind treatment			Open-label treatment						End of treatment	Follow-up	TPD 16 week FU	TPD 52 week FU			
				4	5	6	7	8	9	10 	11	12 	13	14 	15 					16	17 	18 
Visit number	1 	2 	3	4	5	6	7	8	9	10 	11	12 	13	14 	15 	16	17 	18 	19	20	10x	19x
Timing of visit (weeks)	-2		0	1	2	3	4	8	12	16	20	24	28	32	36	40	44	48	52	54	16	52
Visit window (days)				±2	±2	±2	±2	±5	±5	±5	±5	±5	±5	±5	±5	±5	±5	±5	±5	-5	±5	±5
Collect menstrual period diary				x	x	x	x	x	x	x	x	x	x	x	x	x	x	x	x	x		
Attend visit fasting 8.1.3		x	x							x						x			x	x 		

Abbreviation list: TPD = trial product discontinuation, FU = follow up, SMBG = self-measured blood glucose, PHQ-9 = Patient Health Questionnaire 9, C-SSRS = Columbia Suicidality Severity Rating Scale, V = visit, BG = blood glucose, IV/WRS = interactive voice/web response system, ECG = electrocardiogram, hsCRP = high sensitivity C reactive protein.

Protocol 4179-protocol-version-5.0.1  
 NN8022 -4179

Protocol: Liraglutide  
 Trial ID: NN8022-4179

UTN: U1111-1162-7884  
 EudraCT no.: 2014-004415-37

Date:  
 Version:

16 July 2020  
 5.0

Status: Final  
 Page: 21 of 125  
 Novo Nordisk

Footer	Description
1	Maximum two weeks between V1 and V3. V2 must be at least 1 day after V1, and V2 must be at least 5 days before V3, to ensure blood samples are available for randomisation.
2	All assessments at V10 should be performed prior to trial medication dispensing, as the trial medication dispensing session in IV/WRS as V10 will un-blind subject's treatment.
3	Home visits possible for subjects treated with liraglutide placebo only.
4	At V2 all pre-existing conditions should be reported as medical history or concomitant illness.
5	Visit can be performed as phone/video conference visit.
6	Only for females of childbearing potential. At V2 and V19 performed as serum pregnancy test and from V3-V18 urine-stick pregnancy test, if applicable 8.5.5 .

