7	Estradiol for female subjects only and testosterone for male subjects only.
8	Subjects must be instructed to withhold their trial product dose until blood sampling is performed.
9	Only for subjects on open-label liraglutide treatment.
10	Tanner staging can be performed up to 2 weeks before V10 and V19.
11	No 8 hour fasting needed before V20. Minimum 2 hours after the last meal, the anti-liraglutide antibody sample at V20 is to be taken.
12	Please review inclusion criterion 7 and exclusion criterion 27 and evaluate whether a local testing for adrenal insufficiency is needed at V1

Protocol: Liraglutide  
Trial ID: NN8022-4179  
UTN: U1111-1162-7884  
EudraCT no.: 2014-004415-37

CONFIDENTIAL

Date: 16 July 2020  
Version: 5.0  
Status: Final  
Page: 22 of 125

Novo Nordisk

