The PK properties of liraglutide (i.e. exposure) in children and adolescents with PWS will be evaluated by population PK modelling, allowing for sparse PK sampling. The sparse sampling is implemented to reduce the burden on trial subjects and their LAR. The number of samples per subject has been chosen to allow for an adequate precision on the individual estimate for apparent clearance, CL/F. This parameter is used to derive exposure (AUC), thus allowing for a comparison with other relevant populations (such as adults with obesity, children with obesity and adolescents with obesity without PWS). Although sampling during the whole dosing interval will give adequate information on CL/F, the timing of sampling in the dosing interval has been optimized (mostly through samples) to improve precision of the CL/F estimate.

Protocol: Liraglutide  
Trial ID: NN8022-4179  
UTN: U1111-1162-7884  
EudraCT no.: 2014-004415-37

~~CONFIDENTIAL~~

Date: 16 July 2020  
Version: 5.0  
Status: Final  
Page: 31 of 125

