### **8.5.8 Anti-liraglutide antibodies**

Blood samples for determination of anti-liraglutide antibodies are collected from all subjects at randomisation (V3) and at the end of the 16-week double-blind period, see section [2](#). Only samples from subjects treated with liraglutide are analysed for anti-liraglutide antibody development. Depending on the number of subjects in the liraglutide treatment arm, baseline (randomisation V3) from subjects in the placebo group may be analysed for the purpose of determination of the assay cut points. At V19 and V20 antibody samples are collected and analysed from subjects treated with liraglutide only.

Blood samples for the determination of anti-liraglutide antibody must be drawn in a fasting state and prior to administering trial product (see section [2](#)). The anti-liraglutide antibody sample at V20 is to be taken minimum 2 hours after the last meal.

Samples are analysed by the special laboratory for anti-liraglutide antibody formation including cross reactivity to endogenous GLP-1. Furthermore samples from the follow up visit (V20) that are found to be positive for anti-liraglutide antibodies will be analysed for neutralising effect against liraglutide. Anti-liraglutide antibody positive samples from V20 that are also found to cross react with endogenous GLP-1 will in addition be analysed for neutralising effect against endogenous GLP-1. The neutralising antibody analyses will be performed by Novo Nordisk A/S. Baseline antibody samples collected at the randomisation visit will be included in the neutralising antibody analyses for assessment of assay cut points. See further information in sections [8.2](#) and [24.2](#).

Protocol: Liraglutide  
Trial ID: NN8022-4179  
UTN: U1111-1162-7884  
EudraCT no.: 2014-004415-37

~~CONFIDENTIAL~~

Date: 16 July 2020  
Version: 5.0  
Status: Final  
Page: 58 of 125

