## 8.7 Other assessments

### 8.7.1 Plasma concentration of liraglutide for pharmacokinetics

Blood samples for assessment of liraglutide plasma concentration are drawn from all subjects during the 16-week double-blind trial period as per section [2](#).

Subjects and subjects' LAR must be instructed to withhold their trial product dose in the morning until blood sampling is performed on the visit.

The subjects and subjects' LAR must be instructed to complete the dosing diary for liraglutide plasma concentration assessment (section [2](#)) and the dose, date and exact time for sampling the blood must be recorded in the eCRF.

The blood sample taken at V20 for liraglutide plasma concentration assessment from subjects treated with liraglutide only is not part of the pharmacokinetic/pharmacodynamic modelling plan (section [17.5](#)). The purpose of this assessment is to preclude any false negative antibody results. Hence recordings in the subject's dosing diary and eCRF are not requested for this sample.

Quality controlled data must be available for review by Development Bioanalysis prior to database lock (DBL).

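### Protocol 8.1.2 allows trial product as usual around fasting visits, but at V10 and V19, both fasting visits, other passages require the dose to be withheld until blood is drawn

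*Protocol*

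**What the plan says.** Section 8.1.2 defines fasting and leaves the list of visits to the flow chart ("Fasting visits are specified in section" 2). It asks that medicines normally taken with or after food wait until blood sampling and weighing are done. The next sentence reads "Trial product can be taken as usual in relation to fasting visits". It carries no exception and does not refer to footnote 8, 8.5.8 or 8.7.1.

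The flow chart row "Attend visit fasting" marks V10 and V19, among others. The row "Liraglutide plasma concentration" has a V10 entry with footnote 8, and the antibody row has a V19 entry with footnotes 8 and 9. Footnote 8 says: "Subjects must be instructed to withhold their trial product dose until blood sampling is performed". Footnote 9 limits the V19 entry to subjects on open-label liraglutide.

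Two text sections repeat the requirement. Section 8.5.8 says that antibody blood "must be drawn in a fasting state and prior to administering trial product". Section 8.7.1, on PK samples in the double-blind period, says that subjects and their representatives "must be instructed to withhold their trial product dose in the morning until blood sampling is performed on the visit".

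**The concern.** A subject who injects in the morning and relies on 8.1.2 may arrive at V10 or V19 already dosed, at a visit where another passage says the dose should have waited. Section 8.1 treats departures from described procedures as protocol deviations, so following one passage can produce a deviation from another.

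Two secondary data streams are involved. V10 supplies the week-16 PK sample for the objective on steady-state exposure, and section 5.2 says that "the timing of sampling in the dosing interval has been optimized" to improve the clearance estimate. V19 supplies the end-of-treatment antibody sample. The protocol treats circulating drug as relevant to antibody results: section 8.7.1 explains that the V20 drug level is there to guard against false negatives. No drug level is scheduled at V19.

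**Working it through.** The documents give no figure to reproduce. The check is a reading of three flow-chart rows against the visit header, then a comparison of the instructions.

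**1. Where fasting visits and the withhold rule overlap**

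- Marked fasting: V2, V3, V10, V16, V19, and V20 (where footnote 11 removes the 8-hour fast).
- PK samples with footnote 8: V4, V5, V6, V8, V9, V10.
- Antibody samples with footnote 8: V19.
- In both sets: V10 and V19 only.

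The other fasting visits raise no conflict. Before V3 no trial product has been taken, because the first dose is given on site at that visit. V16 has no PK or antibody sample. V20 follows the end of treatment.

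**2. The instructions side by side**

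| Visit | 8.1.2 | Footnote 8 | 8.7.1 | 8.5.8 |
|---|---|---|---|---|
| V10, PK sample | dose permitted as usual | withhold until sampled | withhold morning dose until sampled | not about PK |
| V19, antibody sample | dose permitted as usual | withhold until sampled | does not apply (double-blind period only) | draw before dosing |

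The V19 row concerns subjects on open-label liraglutide only.

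**3. An antibody sample at V10**

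Section 8.5.8 also calls for antibody blood from all subjects at the end of the double-blind period. The antibody row, as read from the PDF, has no V10 mark. That may be a table-reading loss: the Tanner row also lacks a V10 mark, although footnote 10 mentions V10. The blood volumes in Table 8–1 fit a V10 antibody sample:

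- PK-only visits such as V4 draw 2.0 mL. V20 (PK plus antibody) draws 7.0 mL, which implies 7.0 − 2.0 = 5.0 mL for antibodies.
- V19 minus V16: 27.0 − 22.0 = 5.0 mL.
- V10 minus V16: 29.0 − 22.0 = 7.0 mL = 5.0 + 2.0.

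This is an inference that assumes the remaining panels are alike at V10, V16 and V19. The V10 conflict does not depend on it, because the PK sample is enough.

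**4. How many subjects, how many samples**

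- Randomised to liraglutide (Table 17–2): 38.
- At the assumed 10% withdrawal by week 16: 38 × 0.90 = 34.2, about 34.
- At the assumed 20% by week 52: 38 × 0.80 = 30.4, about 30.
- Section 5.3 allows injection at any time of day, and the share who inject before a morning visit is not given. The possible range is therefore 0 to about 34 at V10 and 0 to about 30 at V19.
- Share of scheduled double-blind PK samples: 1/6, about 17% per subject.

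**5. What is recorded**

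The dosing diary (8.7.3.1) covers the last three days before a visit with a PK sample, and 8.7.1 records the exact sampling time. V10 is covered. V19 has no PK sample, so the diary does not reach it. A V19 antibody sample drawn after dosing could not be identified from the diary or from a drug level. The planned antibody summary in SAP 5.4.1.3 is by visit and takes no account of time since dose.

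**The case against.** The strongest answer is that 8.1.2 is a general permission and the other passages are specific requirements. It follows a sentence on medicines tied to meals, and section 5.3 says injections may be given irrespective of meals. The likely intent is that fasting alone is no reason to delay the injection. The wording is also permissive, so it should not be read as telling families to inject before the visit. This is plausible as intent, but the text does not say it. Neither document states which passage prevails, and the contrast with the preceding sentence, which does make other medicines wait for blood sampling, invites the literal reading.

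A reader might infer that the exposure objective is compromised. The documents do not support that. The same sentence of 5.2 that mentions optimised timing says sampling across the whole dosing interval gives adequate information on clearance. Section 17.6 pre-defines no time of day, and the endpoint is a model-derived AUC using recorded times. This part of the objection stands.

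A reader might also infer that V19 antibody results drawn after dosing would be false negatives beyond repair. That is not shown either. The documents give no drug tolerance for the assay and no measure of what a same-day dose adds in a subject already on daily treatment. V20 supplies a later antibody sample, two weeks after the end of treatment, with a drug level. This mitigation is real but partial: results are summarised at each visit, and section 24.2 sends V19 antibody-positive samples for further analysis, so V19 has uses that V20 does not replace.

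**Conclusion.** The contradiction is in the current text and is unresolved. It concerns exactly two visits: V10, through the PK sample, and V19, through the antibody sample in open-label liraglutide subjects. A V10 antibody sample is called for by 8.5.8, but its flow-chart mark cannot be confirmed from the extracted table.

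The consequence is limited. The PK effect is small. The antibody effect cannot be sized from the documents and is partly covered by V20. The number of subjects affected could be none or, on the plan's withdrawal assumptions, as many as about 34 at V10 and 30 at V19. The co-primary analyses, the sample size and the efficacy conclusions are not touched. The point is worth correcting because the correction is cheap and, at V19, samples that fail the 8.5.8 condition cannot currently be told apart from those that meet it.

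**What to change.** The sponsor must reconcile section 8.1.2 with flow chart footnote 8, section 8.5.8 and section 8.7.1, so that sites give families one instruction for V10 and one for V19. Which instruction is right is the sponsor's decision. While doing so, the sponsor should confirm in the flow chart whether an antibody sample is scheduled at V10.

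The date and time of the last dose before the V19 antibody sample should also be recorded in the eCRF, so that samples not meeting the 8.5.8 condition can be identified when antibody results are summarised.

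The cost is one reconciled sentence and one additional eCRF time field. The field is a small extra task for sites; no extra visit or blood draw is needed.
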